#### **Prior/Concurrent Clinical Study Experience**

- 17 Participation in another clinical study with a cytotoxic, investigational product, or other anti-cancer drug for the treatment of advanced NSCLC if received study intervention from that study within 14 days of the first dose of study intervention.
- 18 Known hypersensitivity to the active or inactive excipients of osimertinib or savolitinib or drugs with a similar chemical structure or class.

### **Other Exclusions**

- 19 Involvement in the planning and/or conduct of the study (applies to both AstraZeneca staff and/or staff at the study site).
- 20 Judgment by the investigator that the patient should not participate in the study if the patient is unlikely to comply with study procedures, restrictions and requirements.
- 21 Previous enrolment in the present study.
- 22 For women only - currently pregnant (confirmed with positive pregnancy test) or breast-feeding.
- 23 Patients unable to provide the required number of samples for MET analysis.

CCI

## **5.3 Lifestyle Considerations**

### **5.3.1 Meals and Dietary Restrictions**

Savolitinib should be taken within 15 minutes after the start of a meal. Osimertinib can be taken with water, with or without food. Osimertinib and savolitinib can be taken together.

On PK days, patients should come to the clinic fasted (the patient should not eat but may drink beforehand) where they will be given a moderate breakfast before dosing (the same breakfast should be given on all PK days).

### **5.3.2 Pregnancy and Contraception**

#### **Women of childbearing potential**

Females of childbearing potential should use reliable methods of contraception from the time of screening until 6 weeks after discontinuing study intervention. Acceptable methods of contraception include full abstinence, tubal ligation, combined oral, transdermal or intra vaginal hormonal contraceptives, medroxyprogesterone injections (eg, Depo-provera), copper-banded intra-uterine devices, hormone impregnated intra-uterine systems and vasectomised partners. All methods of contraception (with the exception of total abstinence) should be used in combination with the use of a condom by their male sexual partner for intercourse.

#### **Males**

Male patients must use a condom during sexual intercourse with a female partner of childbearing potential during the study and for 24 weeks after discontinuing study

intervention.

Male patients should refrain from donating sperm from the start of dosing until 24 weeks after discontinuing study intervention.

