## Reproduction

- 18 Females of childbearing potential should be willing to use adequate contraceptive measures, should not be breastfeeding, and must have a negative pregnancy test if of childbearing potential, or must have evidence of non-childbearing potential by fulfilling one of the following criteria at screening:
- Post-menopausal is defined as aged more than 50 years and amenorrhoeic for at least 12 months following cessation of all exogenous hormonal treatments.
  - Women under the age of 50 years would be considered postmenopausal if they have been amenorrhoeic for 12 months or more following cessation of exogenous hormonal treatments and with luteinizing hormone and follicle stimulating hormone levels in the post-menopausal range for the institution.
  - Women with documentation of irreversible surgical sterilisation by hysterectomy, bilateral oophorectomy or bilateral salpingectomy but not tubal ligation.

Further information is available in [Appendix G](#) (Definition of WOCBP and Acceptable Contraceptive Methods).

- 19 Male patients with a female partner of childbearing potential should be willing to use barrier contraception during the study and for 6 months following discontinuation of study intervention. Patients should refrain from donating sperm from the start of dosing until 6 months after discontinuing study intervention.

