#### **8.3.11.2 Paternal Exposure**

Male patients should refrain from fathering a child or donating sperm during the study and 6 months following the last dose.

Pregnancy of the patient's partner is not considered to be an AE. However, the outcome of all pregnancies (spontaneous miscarriage, elective termination, ectopic pregnancy, normal birth or congenital abnormality), occurring from the date of the first dose until 6 months after the last dose and as indicated by previous studies (pre-clinical and clinical) should, if possible, be followed up and documented in the Pregnancy Report Form.

To capture information about a pregnancy from the partner of a male patient, the male patient's partner's consent must be obtained to collect information related to the pregnancy and outcome; the male patient should not be asked to provide this information. A consent form

specific to this situation must be used. The outcome of any conception occurring from the date of the first dose until 4 months after dosing ends should be followed up and documented.

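### Section 8.3.11.2 sets two limits, 6 months and 4 months, for following partner pregnancies; the 24-week male precautions in Section 5.3.2 and the 30-day limit in Section 6.7 should be harmonised with it

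*Supplement*

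**What the plan says.** All the text below is current body text of the protocol (Amendment 2).

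**Follow-up of partner pregnancies**
- Section 8.3.11.2, second paragraph: outcomes of pregnancies "occurring from the date of the first dose until 6 months after the last dose" are to be followed and documented, with the qualifier that this be done where possible.
- Section 8.3.11.2, last sentence: "The outcome of any conception occurring from the date of the first dose until 4 months after dosing ends" is to be followed up and documented, without that qualifier.
- Section 8.3.11, the parent section: all pregnancies and their outcomes go to the sponsor. The only exception is a pregnancy found before the patient has had any study intervention. No end date is given.
- Appendix A 3: a partner who becomes pregnant up to 6 months after the study is asked to consent and give information about the pregnancy.
- Section 6.7: for patients who stay on treatment after the final analysis, pregnancies are reported until 30 days after the last dose.

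**Precautions for men**
- Section 5.3.2: condoms "during the study and for 24 weeks after discontinuing study" intervention, and "Male patients should refrain from donating sperm from the start of dosing until 24 weeks after" discontinuation.
- Inclusion 19: men should be willing to use "barrier contraception during the study and for 6 months following discontinuation of study intervention"; also "Patients should refrain from donating sperm from the start of dosing until 6 months after discontinuing study intervention".
- Section 8.3.11.2: "Male patients should refrain from fathering a child or donating sperm during the study and 6 months following the last dose".

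**Women, for comparison**
- Section 5.3.2: contraception "from the time of screening until 6 weeks after discontinuing study intervention". Section 8.3.11.1 uses the same 6 weeks, after the last dose, for pregnancy reporting.

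**The concern.** Instructions on exposure of partners and the foetus should carry one period, because a site will act on whichever sentence it reads. Under Section 8.3.11.2 a conception in the fifth or sixth month after dosing falls inside one sentence and outside another in the same section. A site working from the last sentence could close its follow-up about two months early.

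The male precautions raise a smaller version of the same problem. Section 5.3.2 is where a site would look for contraception advice, and nothing there signals that Inclusion 19 and Section 8.3.11.2 state the period differently. The instructions remain live although recruitment has ended, since Section 6.7 lets patients continue treatment beyond the final data cut-off.

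No endpoint, analysis set or sample size depends on any of this.

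**Working it through.** The plan states no derived figure here, so there is nothing to reproduce. The check is calendar arithmetic plus a side-by-side reading.

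**Inputs.** 24 weeks (Section 5.3.2); 6 months (Inclusion 19, Section 8.3.11.2); 4 months (Section 8.3.11.2, last sentence); 30 days (Section 6.7); 6 weeks (Sections 5.3.2 and 8.3.11.1). The protocol does not define a month, so three readings are tried. The 30-day and 28-day months are assumptions; the second borrows the length of the 28-day treatment cycle.

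**Lengths in days**
- 24 weeks: 24 × 7 = 168.
- Calendar months, taking every start date from 2021 to 2024: 6 months = 181 to 184; 4 months = 120 to 123.
- 30-day months: 6 × 30 = 180; 4 × 30 = 120.
- 28-day months: 6 × 28 = 168; 4 × 28 = 112.

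| Reading of a month | 6 months minus 4 months (Section 8.3.11.2) | 6 months minus 24 weeks (Section 5.3.2) |
|---|---|---|
| Calendar | 59 to 62 | 13 to 16 |
| 30 days | 180 − 120 = 60 | 180 − 168 = 12 |
| 28 days | 168 − 112 = 56 | 168 − 168 = 0 |

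The calendar gap of 59 to 62 days was computed start date by start date. The conflict inside Section 8.3.11.2 is therefore 56 to 62 days on every reading tried. The Section 5.3.2 gap runs from 0 to 16 days and depends on the reading.

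**Section 6.7.** Six weeks is 42 days, so the 30-day limit is 42 − 30 = 12 days shorter than the maternal window. Against a 6-month partner window it is 168 − 30 = 138 days shorter with 28-day months, and up to 184 − 30 = 154 days shorter with calendar months.

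**Which follow-up limit is better supported?** Section 8.3.11 has no limit, Appendix A 3 uses 6 months (counted from the study, not the last dose), and the first paragraph of Section 8.3.11.2 asks men not to father a child for 6 months. None of these uses 4 months.

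**The case against.** **The two follow-up sentences may be nested.** The 6-month sentence is qualified and the 4-month sentence is not, so one could read firm follow-up to 4 months and best effort to 6. That reading is possible, but the protocol states no such scheme and a site would have to supply it.

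**Other text already covers months 4 to 6.** This largely stands. A reader might infer that a conception in that interval would go unrecorded. The documents do not support that: Section 8.3.11 requires reporting without a time limit, and Appendix A 3 provides for partner consent. What remains is a sentence that invites earlier closure.

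**24 weeks may simply mean 6 months.** This also stands in part. It is tempting to give a 13-to-16-day shortfall as fact, but that holds only for calendar months. With 28-day months there is no gap, and loose rounding is a plausible explanation.

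**Inclusion 19 is an entry criterion.** On contraception it tests only willingness; the operative condom rule is in Section 5.3.2. The sperm-donation sentence in Inclusion 19 is itself an instruction, so that comparison is direct.

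**The longest period satisfies everything.** This is true of the male precautions and of the two partner limits in Section 8.3.11.2: a site that keeps to 6 months breaches neither. It limits the consequence but does not make the shorter statements right.

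**Conclusion.** The main point holds: Section 8.3.11.2 gives two limits for following partner pregnancies, 56 to 62 days apart on any of the three readings of a month, and the rest of the protocol favours the longer one. The 24 weeks in Section 5.3.2 is a secondary harmonisation, worth 0 to 16 days depending on what a month means.

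Because the maternal windows in Sections 5.3.2 and 8.3.11.1 agree, a reader might conclude that the mismatch is confined to the text for men and partners. It is not: the 30-day limit in Section 6.7 departs from both the maternal and the partner windows. Nor can it be said that men are being told the wrong period, because the patient information is not shown.

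This is a minor safety correction, suitable for the next amendment, with no bearing on the statistical design or analysis.

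**What to change.** 1. In the last sentence of Section 8.3.11.2, change 4 months to 6 months.
2. In both male statements of Section 5.3.2, change 24 weeks to 6 months, to match Inclusion 19 and Section 8.3.11.2.
3. In Section 6.7, align the 30-day pregnancy-reporting limit with the 6-week maternal and 6-month partner windows.
4. Check that the patient information carries the same periods.

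The cost is wording in the protocol and, if needed, the patient information. Partner follow-up under item 1 lengthens by 56 to 62 days relative to the last sentence as it stands, which the 6-month sentence already asks for where possible. Item 3 lengthens pregnancy reporting for patients treated beyond the final analysis. Trial data, analysis and sample size are unaffected.

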### **5.3.3 Other Lifestyle Restrictions**

For savolitinib, during the study therapy and for 4 weeks after the last dose of study intervention patients should be advised to avoid prolonged exposure to the sun, wear protective clothing, a hat and seek shade from the sun as far as possible; in addition sun protection factor 30+ sunscreen should be used. Exposure to other sources of ultraviolet light including sun beds and tanning booths, etc, should be avoided.

Patients should not donate blood or blood products during the study.

## **5.4 Screen Failures**

Screen failures are defined as patients who consent to participate in the clinical study but are not subsequently randomly assigned to study intervention. A minimal set of screen failure information is required to ensure transparent reporting of screen failure patients to meet the Consolidated Standards of Reporting Trials publishing requirements and to respond to queries from regulatory authorities. Minimal information includes demography, screen failure details, MET status information, eligibility criteria, and any SAEs.

Individuals who do not initially meet the criteria for participation in this study (for example, due to logistical constraints or slow recovery of side effects from previous treatment; ie, screen failures) may be rescreened. Rescreened patients retain the same patient number as for the initial screening. However, rescreening assessments should be documented so that its effect on study results, if any, can be assessed.

These patients should have failed inclusion/exclusion criteria and the reason for study withdrawal recorded in the eCRF.

Pre-screen failures are defined as patients who signed the pre-screening ICF but are not confirmed as MET amplified by central laboratory testing. If the patient is subsequently pre-screened again the same patient number as for the initial pre-screening will be retained.

## **6 STUDY INTERVENTION**

Study intervention is defined as any investigational intervention(s), marketed product(s), placebo, or medical device(s) intended to be administered to a study patient according to the CSP.

## **6.1 Study Interventions Administered**

### **6.1.1 Investigational Products**

Refer to [Table 5](#) for information regarding the study interventions.

**Table 5 Investigational Products**

Intervention name	Savolitinib	Osimertinib/Placebo
Type	Drug	Drug/Placebo
Dose Formulation	Tablet	Tablet
Dosage level	
CCI savolitinib (CCI tablets CCI)
	
CCI osimertinib/placebo (CCI tablet CCI)
 
CCI osimertinib/placebo tablets are available if a dose reduction is required

Route of administration	Oral	Oral
Dosing instructions	
Savolitinib will be taken CCI within 15 minutes after the start of a meal except for the day on which PK samples are taken when savolitinib will be taken within 15 minutes after a meal prepared by the clinic.
 
CCI
 
Doses should not be missed. If a patient misses taking a scheduled dose, within a window of 12 hours, it is acceptable to take the dose. If it is more than 12 hours after the scheduled dose time, the missed dose should not be taken, and patients should be instructed to take the next dose at the next scheduled time. If a patient vomits after taking their study intervention, they should not make up for this dose, but should take the dose at the next scheduled time.
	
Osimertinib will be administered CCI with or without food except for the day on which PK samples are taken when osimertinib will be taken after a meal prepared by the clinic.
 
CCI
 
Doses should not be missed. If a patient misses taking a scheduled dose, within a window of 12 hours, it is acceptable to take the dose. If it is more than 12 hours after the scheduled dose time, the missed dose should not be taken, and patients should be instructed to take the next dose at the next scheduled time. If a patient vomits after taking their study intervention, they should not make up for this dose, but should take the dose at the next scheduled time.

Sourcing	AstraZeneca	AstraZeneca
Packaging and labelling	CCI	CCI
Current/former names	CCI	CCI

CCI CCI PK = Pharmacokinetics.

## **6.2 Preparation/Handling/Storage/Accountability of Interventions**

The investigator or designee must confirm appropriate temperature conditions have been maintained during transit for all study intervention received and any discrepancies are reported and resolved before use of the study intervention.

Only patients enrolled in the study may receive study intervention and only authorised site staff may supply or administer study intervention. All study intervention must be stored in a secure, environmentally controlled, and monitored (manual or automated) area in accordance with the labelled storage conditions with access limited to the investigator and authorised site staff.

The investigator, institution, or the head of the medical institution (where applicable) is responsible for study intervention accountability, reconciliation, and record maintenance (ie, receipt, reconciliation, and final disposition records).

Further guidance and information for the final disposition of unused study interventions are provided in the Pharmacy Manual.

## **6.3 Measures to Minimise Bias: Randomisation and Blinding**

Patient eligibility will be established before treatment randomisation. Once the eligibility of a patient has been confirmed, the investigator (or nominated assistant) should contact the IVRS/IWRS Centralised Randomisation Centre for allocation of randomised therapy.

All patients will be centrally assigned to randomised study intervention using an IVRS/IWRS. Before the study is initiated, the telephone number and call-in directions for the IVRS and/or the log in information and directions for the IWRS will be provided to each site. Patients will be randomised in a 1:1 ratio with stratification according to the number of prior lines of therapy (ie, osimertinib monotherapy as first line or  $\geq$  second line [which includes patients who received osimertinib monotherapy as first line therapy followed by chemotherapy or osimertinib monotherapy after chemotherapy]). If a patient withdraws from the study, then his/her enrolment/randomisation code cannot be re-used. Withdrawn patients will not be replaced.

It is recommended that patients commence study intervention as soon as possible after randomisation, and ideally within 3 days. Patients will complete treatments as specified above or until disease progression is confirmed, unacceptable toxicity occurs, withdrawal of consent, or another discontinuation criterion is met.

The IVRS/IWRS will provide to the investigator(s) or pharmacists the kit identification number to be allocated to the patient at the dispensing visit. Routines for this will be described in the IVRS/IWRS user manual that will be provided to each centre.

The randomisation code can be broken after investigator-assessed PD per RECIST 1.1. Patients initially randomised to the savolitinib plus placebo arm may then be offered the opportunity to cross-over to receive savolitinib in combination with osimertinib. Once the investigator has documented progression in the eCRF, and obtained approval for unblinding from the study physician, the treatment code for a patient may be obtained from the IWRS via a dedicated option they may select in this situation. In all other circumstances the randomisation code should not be broken except in medical emergencies when the appropriate management of the patient requires knowledge of the treatment randomisation. The investigator documents and reports the action to AstraZeneca, without revealing the treatment given to the patient to the AstraZeneca staff.

AstraZeneca retains the right to break the code for SAEs that are unexpected and are suspected to be causally related to an investigational product and that potentially require expedited reporting to regulatory authorities. Randomisation codes will not be broken for the planned analyses of data until all decisions on the evaluability of the data from each individual patient have been made and documented.

The IWRS/IWRS will be programmed with blind-breaking instructions. In case of an emergency, in which the knowledge of the specific blinded study intervention will affect the immediate management of the patient's condition (eg, antidote available), the investigator has the sole responsibility for determining if unblinding of a patients' intervention assignment is warranted. Patient safety must always be the first consideration in making such a determination. If a patient's intervention assignment is unblinded, the sponsor must be notified within 24 hours after breaking the blind. The investigator documents and reports the action to AstraZeneca, without revealing the treatment given to the patient to the AstraZeneca staff. Additionally, patients with investigator-assessed objective PD may be unblinded.

Prior to CSP V3.0, the AstraZeneca study team was to be unblinded at the time of the primary analysis. Under CSP V3.0, following the early termination of study recruitment, an initial DCO will occur to allow an early review of the data. The study will be unblinded after data cleaning activities on this initial DCO data have been completed.

The personnel analysing the PK samples will be unblinded to the investigational treatment for each patient.

Returned study intervention should not be re-dispensed to the patients.

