#### **4.1.4 Early Study Recruitment Termination**

On 22 February 2022, AstraZeneca made the decision to terminate study recruitment. This was based on programme development strategy considerations, because the design of the contribution of component study is no longer supportive of the savolitinib development programme in this study population. The contribution of component of savolitinib monotherapy (savolitinib plus placebo to osimertinib) versus savolitinib in combination with osimertinib will continue to be assessed in the ongoing SAVANNAH study. Following early termination of study recruitment, an initial DCO will occur to allow an early review of the

data by AstraZeneca. The study will be unblinded after completion of data cleaning activities on the initial DCO data, and patients on savolitinib monotherapy (savolitinib plus placebo) will be given the opportunity to cross-over to the savolitinib plus osimertinib arm. Patients may otherwise choose to remain on savolitinib monotherapy (as long as, in the opinion of the investigator, they are still receiving clinical benefit and have not reported PD). All patients will be followed until the final analysis. Patients already in pre-screening/screening (who have signed the pre-screening/main ICF) at the time of study recruitment termination will have the option to be randomised if eligible. The final DCO will occur 9 months after the last patient has been randomised. Following the final database lock, any patients who are still on the savolitinib plus placebo arm will be given the opportunity to cross-over to the savolitinib plus osimertinib arm. Randomised patients may continue to receive their assigned treatment for as long as they are deriving clinical benefit, or until they meet any discontinuation criteria, and will be monitored according to routine clinical practice as defined by the investigator. For the definition of the end of the study please see Section 4.4. For access to study intervention after the end of the study please see Section 6.7.

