**9 STATISTICAL CONSIDERATIONS**

**9.1 Statistical Hypotheses**

The primary objective of this study is to assess the ORR of savolitinib in combination with osimertinib versus savolitinib in combination with placebo in patients with EGFRm+, MET amplified locally advanced or metastatic NSCLC who have progressed on previous osimertinib therapy. The null hypothesis is that there is no difference between treatment groups on ORR based on investigator assessment per RECIST 1.1 when all patients have had the opportunity to be treated for 6 months. The alternative hypothesis is that there is a difference between treatment groups in this regard.

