#### **9.4.1.2 Multiplicity Strategy for Primary and Key Secondary Endpoints**

Prior to CSP V3.0, the primary analysis was to occur 6 months after the last patient was randomised. This will be based on a comparison of the primary endpoint (ie, ORR) between treatment groups and will be tested at the 2-sided 5% significance level.

CCI [REDACTED] the secondary efficacy endpoints will be tested at a 2-sided significance level of 5%. There will be no adjustment for multiplicity as the study is not designed to support labelling claims on any of the endpoints.

Final analysis was to be performed after the earlier of 18 months after the last patient was randomised or when 70% of the patients have progressed or died due to any cause. CCI [REDACTED]

Under CSP V3.0, as a result of AstraZeneca's decision to terminate study recruitment early, there will be no primary analysis at the originally planned timepoint. Following early termination of study recruitment, an initial DCO will occur to allow an early review of data by AstraZeneca. A final DCO will occur 9 months after the last patient has been randomised, after which the final analysis will be performed. CCI [REDACTED]

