### **Central Review of RECIST 1.1 Based Assessments**

The BICR of radiological imaging data will be carried out using RECIST 1.1. All radiological scans for all patients (including those unscheduled visits, or outside visit windows) will be provided to the BICR. The imaging scans will be reviewed by 2 independent radiologists using RECIST 1.1 criteria and will be adjudicated if required. The independent reviewers will be blinded to study intervention. Blinded independent central review data will be used to determine endpoints: ORR and PFS as a sensitivity analysis.

Further details of the BICR will be documented in the BICR charter.

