#### **9.4.2.1 Analysis of Primary Endpoint**

Objective response rate by investigator assessment in accordance with RECIST 1.1 is the primary endpoint for this study.

The ORR is defined as the proportion of patients with an investigator-assessed response of CR or PR by RECIST 1.1.

Data obtained up until progression, or last evaluable assessment in the absence of progression, will be included in the assessment of ORR. Patients who discontinue treatment without progression, receive a subsequent anti-cancer therapy (note that for this analysis radiotherapy is not considered a subsequent anti-cancer therapy) and then respond will not be included as responders in the ORR.

The ORR will be analysed using a logistic regression model adjusting for the stratification used in the randomisation. The results of the analysis will be presented in terms of an odds ratio (an odds ratio greater than 1 will favour savolitinib in combination with osimertinib versus savolitinib in combination with placebo) together with its associated profile likelihood 95% CI and p-value (based on twice the change in log-likelihood resulting from the addition of a treatment factor to the model).

If there are not enough responses for a meaningful analysis using logistic regression then a CMH test will be presented.

Summaries will be produced that present the number and percentage of patients in each treatment group with a tumour response (CR/PR).

A sensitivity analysis of the ORR will be performed based on the BICR assessment of disease progression by RECIST 1.1. Further sensitivity analyses will be described in the SAP.

Summaries will be produced that present the number and percentage of patients in each treatment group with a tumour response (CR/PR). Summaries will also be produced for ORR per BICR.

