### **H 2.9.5      Central Imaging**

Images, including unscheduled visit scans, will be collected on an ongoing basis and sent to an AstraZeneca-appointed imaging CRO for quality control, storage, and for BICR. Guidelines for image acquisition, de-identification, storage of digital copies at the investigative site (as source documents), and transfer to the imaging CRO will be provided in a separate document. Electronic image transfer from the sites to the imaging CRO is strongly encouraged. A BICR of images will be performed at the discretion of AstraZeneca. Results of these independent reviews will not be communicated to investigators, and results of investigator RECIST 1.1 assessments will not be shared with the central reviewers. The management of patients will be based in part upon the results of the RECIST 1.1 assessment conducted by the investigator. Further details of the BICR will be documented in the Independent Review Charter.

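### After the unblinding planned in protocol version 3.0, savolitinib-plus-placebo patients who switch without progression have their ORR data cut off while everyone else accrues locally read responses to the final data cut-off

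*Supplement*

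**What the plan says.** Section 9.4.2.1 fixes the endpoint and the assessor: "Objective response rate by investigator assessment in accordance with RECIST 1.1 is the primary endpoint for this study". It counts data up to progression or, failing that, the last evaluable assessment. It sets no stop at unblinding.

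Under protocol version 3.0 (Amendment 2), Section 9.4.1.2 states that "there will be no primary analysis at the originally planned timepoint", and then: "A final DCO will occur 9 months after the last patient has been randomised, after which the final analysis will be performed". Unblinding comes before that point. Section 6.3 says of the initial DCO: "The study will be unblinded after data cleaning activities on this initial DCO data have been completed". Section 4.1.4 adds that "patients on savolitinib monotherapy (savolitinib plus placebo) will be given the opportunity to cross-over to the savolitinib plus osimertinib arm". Section 8.1.1 and Table 2 (footnote h) show that this includes patients without objective progression, because they set a scan schedule for exactly those patients.

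Section 9.4.1 governs what happens to switchers' data. For any S+P assessment, it stops at the last assessment before the first combination dose. No matching stop is written for S+O. Sections 4.1.2 and 4.1.4 also let S+P patients stay on monotherapy and have all patients followed to the final analysis.

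On central review, the 9.4.2 text says: "Blinded independent central review data will be used to determine endpoints: ORR and PFS as a sensitivity analysis". Section 9.4.2.1 likewise commits to a BICR sensitivity analysis of ORR. Appendix H 2.9.5 says: "A BICR of images will be performed at the discretion of AstraZeneca".

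**The concern.** While cross-over required progression, the Section 9.4.1 cut did no harm to ORR: counting ends at progression in both arms anyway. Version 3.0 opens switching to patients who have neither progressed nor, in some cases, yet responded. For those patients the cut removes time in which they could still have responded on S+P, while a comparable S+O patient remains at risk of a first response until the final DCO.

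The second element is the reading. Offering the switch reveals the arm to the site, so any response first seen after unblinding is a local reading by an investigator who can know the treatment. Sections 4.1.2 and 6.3 have evaluability decisions documented before unblinding, but that cannot cover scans not yet taken.

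The unequal window lowers observed S+P ORR only. Open-label reading could add to the gap, although its direction and size cannot be read from the documents. What is at stake is whether a difference in the primary endpoint reflects treatment or partly the rules for counting.

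**Working it through.** **Plan figures open to checking.** The power statement is redacted, and the plan gives no figure for this issue. The only response probabilities shown, for the superseded futility rule, reproduce: 0.95^10 = 0.599, 0.90^10 = 0.349, 0.57^10 = 0.004. They do not bear on the point.

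**Whose late first responses count under the written rules**

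| Patient after unblinding, not progressed | First response after unblinding counts in randomised arm? | Local reader can know arm? |
|---|---|---|
| S+O | Yes, to final DCO | Yes |
| S+P, stays on monotherapy | Yes, to final DCO | Yes |
| S+P, switches | No, cut at the switch | Not applicable |

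The asymmetry lies wholly in the third row.

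**Illustrative size.** Assume the same true ORR, p, in both arms. Let f be the share of first responses that would fall after unblinding, and c the share of those S+P patients who switch first. A patient whose data are cut stays in the full analysis set as a non-responder. Then:

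- observed S+O ORR = p
- observed S+P ORR = p × (1 − f × c)
- built-in gap = p × f × c

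Only p has an anchor in the documents: Section 4.2.1 cites 30% (95% CI 20 to 43) for the combination in an earlier study. The values of f and c are assumptions.

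- Low end: 0.20 × 0.10 × 0.50 = 0.01, or 1 point.
- High end: 0.40 × 0.30 × 1.00 = 0.12, or 12 points.

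At p = 30%:

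| f | c | Observed S+P ORR | Gap (points) | Rejection rate, 28 per arm | Rejection rate, 20 per arm |
|---|---|---|---|---|---|
| 0 | – | 30.0% | 0 | 5.2% | 5.4% |
| 10% | 50% | 28.5% | 1.5 | 5.3% | 5.5% |
| 10% | 100% | 27.0% | 3.0 | 5.8% | 5.8% |
| 20% | 50% | 27.0% | 3.0 | 5.8% | 5.8% |
| 20% | 100% | 24.0% | 6.0 | 8.0% | 7.3% |
| 30% | 50% | 25.5% | 4.5 | 6.7% | 6.4% |
| 30% | 100% | 21.0% | 9.0 | 11.8% | 10.2% |

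The rejection rates come from exact enumeration of two binomials with a pooled two-sided z-test at 5%, standing in for the planned likelihood-ratio test. They matter only if such a test is run on final-DCO data. The planned 28 per arm will not be reached. At 10 per arm the rate runs from 3.8% with no late responses to 5.4% at f = 30%, c = 100%, so in a very small trial the distortion shows in the estimate more than in the error rate.

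**Reader effect.** One additional responder in one arm moves its ORR by 1/28 = 3.6 points, 1/20 = 5 points or 1/10 = 10 points.

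**After a common cut.** If ORR in both arms stops at unblinding, f = 0 by construction and the built-in gap is zero.

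**The case against.** Several points on the other side stand.

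- A reader might infer that late responses count in one arm only. They do not: S+P patients who stay on monotherapy keep contributing, so the imbalance is partial and depends on uptake.
- The size rests on assumed inputs. The first four scans fall at weeks 6, 12, 18 and 24, and the dropped futility look relied on two scans. If most first responses come early, f is small and the effect may be negligible. Once recruitment stopped, only patients already in pre-screening or screening could be added.
- Reader bias is partly handled. Two blinded radiologists, with adjudication if required, supply a BICR ORR. That analysis still inherits the cut on switchers.
- A reader might also infer that the Section 9.1 hypothesis can no longer be met, since it refers to the time "when all patients have had the opportunity to be treated for 6 months". That reading is weak: the final DCO is at 9 months, and a voluntary switch does not take away an opportunity.
- Text beside the final-analysis statements is redacted, and no SAP is shown. Either may already hold a sensitivity analysis of this kind.
- The trial stopped recruiting early, and Section 9.4.1.2 says it was not designed to support labelling claims, which limits the consequences.

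None of this removes the unequal windows that follow from Sections 4.1.4, 8.1.1, 9.4.1 and 9.4.2.1 read together.

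**Conclusion.** The concern holds in a limited form. Under the rules as written, S+P patients who switch without progression lose the remainder of their response window. All other non-progressing patients keep theirs to the final DCO, with local readings that are no longer blinded. The effect of the cut on ORR favours S+O. The illustration gives about 1 to 12 points when there is no true difference, and 6 points (24% against 30%) at 30% ORR, 20% late first responses and complete switching, which is the extreme for uptake. These figures show scale and are not estimates for this trial, whose initial DCO date, actual sample size, number at risk and uptake are not stated.

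The documents do not support going further and calling for the final-DCO analysis to be replaced. Patients randomised last could have few or no post-baseline scans before unblinding, so a pre-unblinding cut has its own weakness as the sole analysis. Nor do they show that BICR will be missing. They show that 9.4.2 and 9.4.2.1 commit to it while Appendix H 2.9.5 leaves it to the sponsor's discretion.

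**What to change.** 1. In Section 9.4.2.1, pre-specify before unblinding an investigator-assessed ORR analysis that uses only assessments dated on or before study unblinding, in both arms. Report it beside the final-DCO result, and state that it will be used to judge whether any difference depends on post-unblinding data.
2. Produce the BICR ORR with the same cut as well as at the final DCO.
3. Reconcile Appendix H 2.9.5 with 9.4.2 and 9.4.2.1 so that BICR ORR is always produced.

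If the SAP already contains the first two items, a cross-reference is enough. The cost is some wording and one or two extra tables. The patients randomised last will contribute fewer scans to the pre-unblinding analysis, so the number of post-baseline assessments per arm should be shown with it. Treatment, access to cross-over and visit schedules are untouched.
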